stress. Basal acyl-carnitines revealed accumulation of many long chain acyl-CoA's in type 2 diabetics including C18:0, C18:2-OH, and C20:4, which are thought to promote insulin resistance (Figure 11A). A significantly decreased GSH/GSSG ratio in type 2 diabetes individuals compared to lean volunteers suggest a more oxidized state, consistent with increased oxidative stress in insulin resistance (Figure 11B).

DAG and ceramide decrease mitochondrial

function. We administered 1,2-DAG, ceramide, dihydroceramide, and vehicle controls to isolated rat mitochondria in vitro to evaluate the impact on mitochondrial respiration using pyruvate and malate as substrates. DAG and ceramide decreased state 3 respiration, with no changes observed with dihydroceramide administration (Figure 12A and B). State 4 respiration did not change for 1,2-DAG and dihydroceramide, but increased significantly with increasing doses of ceramide. Both 1.2-DAG and ceramide decreased ADP/O ratios (Figure 13A and B), while dihydroceramide had no effect. These data indicate 1.2-DAG and ceramide reduced mitochondrial respiration and coupling, and are consistent with accumulation of mitochondrial lipids altering mitochondrial function.

Protocol Template CF-146, Effective 7/10/11

IV. Research Methods

A. Outcome Measure(s):

Primary outcomes:

Aim 1: Change in insulin sensitivity, change in sarcolemmal Di-C18:0 DAG and C18:0 ceramide, change in PKCepsilon and PP2A activity

Aim 2: Change in insulin sensitivity, change in mitochondrial/ER total DAG and ceramide content, change in state 3 mitochondrial respiration, change in GSH/GSSG, change in C18:0, C18:2-OH, and C20:4 acylcarnitines, change in GRP78

Aim 3: Change in mitochondrial state 3 and state 4 respiration in response to DAG and ceramide before and after lifestyle interventions

Secondary outcomes: Changes in other localized lipids and intracellular responses will be exploratory in nature. In addition, we will collect subjective and objective information about sleep and an exploratory analysis.

B. Description of Population to be Enrolled:

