Obese men and women (BMI 30-40 kg/m²) will be recruited for this study who are between 30-50 years of age and sedentary (<2 hours/week of planned physical activity). Individuals with normal glucose tolerance (NGT), pre-diabetes, and newly diagnosed type 2 diabetes will be enrolled. Normal glucose tolerance is defined as a HbA1c of <5.7%, pre-diabetes as a HbA1c of 5.7-6.4%, and type 2 diabetes as a HbA1c of \geq 6.5% (31). Oral contraceptive use is allowed as long as women don't change their use, or lack thereof, during the course of the study. Exclusion criteria include: regular exercise more than 2 hours/week, medications that could affect glucose, lipid metabolism, thyroid disease, a history of lung disease, pregnancy, active cigarette smoking and severe plasma lipid disorders.

Inclusion criteria:

BMI: 30-40 kg/m²
Age: 30-50 years
Planned physical activity: <2 hrs/week
Glucose tolerance: NGT, pre-diabetes, and Type 2 diabetes
Normal glucose tolerance (NGT) is defined as HbA1c of <5.7%, pre-diabetes as HbA1c of 5.7-6.4%, and type 2 diabetes as HbA1c of ≥6.5% (31).
Oral contraceptive use: Yes or No as long as there is no change during the study
Medications: not taking TZD's, insulin
Thyroid status: TSH between 0.5-5.0 mU/L
Pregnancy status: Not pregnant
Nonsmoker (tobacco and any form of marijuana use)
Fasting TG <400mg/dl
FSH < 20 IU/L

C. Study Design and Research Methods

Ninety-two individuals (30-50 years old) will be screened to recruit sixty-nine obese men and women into the study. Individuals with and without prediabetes will be recruited to achieve a range of starting insulin sensitivities without confounding effects of medications used to treat type 2 diabetes. Volunteers will undergo an insulin clamp before and after block randomization by sex and pre-diabetes strata equally across intervention groups, into a three month

intervention consisting of: 1) endurance exercise training without weight loss, 2) diet-induced weight loss, or 3) delayed intervention control (Figure 5). The three month intervention will result in significant gains in fitness, weight loss, and improvements in insulin sensitivity, but is short enough to maximize retention.

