Muscle biopsy – Subcellular fractionation will be performed as described in Figure 1. Diacylglycerol (1,2- and 1,3- isomers), sphingolipids (dihydroceramide, ceramide, glucosylceramide, lactosylceramide, sphingosine, sphingosine-1-phosphate, sphingomyelin), triacylglycerol, phosphatidic acid, and long chain acyl-CoA species will be analyzed by [name] using the lipidomics platform in our laboratory. Subcellular fractions are fortified with internal standards (ISs), lipid extracted, and analyzed by an Agilent 1100 HPLC connected to an API 2000 triple quadrupole mass spectrometer (40). The 1,3- and 1,2- DAG isomers are separated chromatographically using a Hilic 2.1 micron, 3x100mm column. Concentration is determined by comparing ratios of unknowns to odd chain or deuterated internal standards. Incorporation of [U-¹³C]glucose into DAG glycerol, and [U-¹³C] palmitate into the sphingolipid backbone will be used to estimate *de novo* synthesis of DAG and sphingolipids (41; 42). Western blot analysis will quantify PKC translocation of θ , ε , β II, and δ isoforms in basal biopsies, as well as insulin signaling in basal and insulin stimulated biopsies including AKT^{ser473} /total, IRS-1^{Tyr612}/total, and AS160^{Thr642}/total using standard techniques (43). AKT^{Thr34} phosphorylation will be used to estimate PKC ζ activation by ceramide. PP2A activity will be measured using manufacturer instructions (Ser/Thr Phosphatase Assay Kit 1, Billerica, MA).

After the baseline clamp, subjects will be randomized into one of three interventions for three months:

1. Endurance exercise training - Participants will undergo supervised endurance exercise training administered by the Nutrition Obesity Research Center (NORC) Energy Balance Core (see attached letter of support from [name]) using well-established methods (44-48). Participants will perform supervised exercise 4x/week as well as exercise 1x/week on their own. Each 60 min session will include a short warm-up, 40 to 50 min of endurance exercise, and a cool-down. The exercise program will consist primarily of brisk walking or jogging, and will be supplemented with rowing, stepping, or elliptical exercise. The initial exercise prescription will be 30 minutes at 65% of maximal HR. During the first 2 weeks of training, exercise duration and intensity will be gradually increased

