Aim 1: Our statistical methods are rigorous with an a priori statistical analysis plan to test our hypothesis in an unbiased manner, and power analysis based on our own preliminary data. Prior to analysis, data will be analyzed for normality, and any non-normally distributed variables will be log-transformed for use in analytic models. Correlations between the change in sarcolemmal DAG and sphingolipid species and the change in insulin sensitivity will be performed using Pearson's correlation coefficients in the entire study group (n=51). Then, data comparing changes in sarcolemmal DAG and sphingolipid species to changes in insulin sensitivity before and after the intervention will be analyzed using a one-way Analysis of Variance (ANOVA) to examine overall differences between the intervention groups, and using Tukey's procedure to make pair-wise comparisons (e.g control vs. exercise, control vs. diet only) while adjusting for multiple comparisons. Changes in individual DAG and ceramide species will be examined using the Benjamini Hochberg procedure to limit false discoveries (62), and then Principal Component Analysis (PCA) will be used to examine groups of DAG and ceramide species (13). Analyses will be conducted using SAS statistical software ver. 9.4 (Cary, NC). The power analysis is based on changes in sarcolemmal lipids assuming there will be no significant changes in the control intervention. With an overall n of 51, we will have 92% power to detect a Pearson correlation coefficient similar to our preliminary data (Figure 2B, r= -0.45), and 80% power to detect a correlation coefficient as small as -0.38. Pilot data showed sarcolemmal C18:0 ceramide decreased 0.041 ng/ug protein with a SD of .02 after the combined intervention. With an n of 17/group we will have 84.6% power to measure a similar change in sarcolemmal DAG and sphingolipids for individual group comparisons using the Tukey procedure. The type 1 error rate (alpha) will be set at 5% for all comparisons.

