Aim 2: Our statistical methods are rigorous with an *a priori* statistical analysis plan to test our hypothesis in an unbiased manner, and power analysis based on our own preliminary data. Data will be analyzed for normality, and any non-normally distributed variables will be log-transformed for use in analytic models. Correlations between the change in mitochondrial/ER DAG and sphingolipid species and the change in insulin sensitivity, mitochondrial respiration, ROS production, acyl-carnitine species, and ER stress will be performed using Pearson's correlations coefficient in the overall study group. Data comparing changes in mitochondrial/ER DAG and sphingolipid species to changes in insulin sensitivity and parameters of mitochondrial respiration between groups before and after the intervention will be analyzed using a oneway ANOVA (SAS statistical software ver. 9.4, Cary, NC). If overall differences are observed by group then individual group comparisons will be made using Tukey's procedure, which corrects for family-wise error rates. Changes in individual DAG and ceramide species will be examined using the Benjamini Hochberg procedure to limit false discoveries, and changes in groups of DAG and ceramide species will be examined using PCA as described in Aim #1. Our power analysis is based on our preliminary data for the change in mitochondrial ceramide and DAG species after the pilot intervention shown in Figures 8 and 10, and assuming there will be no significant changes in the control intervention. With an overall n of 51, we will have 99% power to detect a Pearson correlation coefficient as large as that observed in our preliminary data (Figure 7B, r= -0.44), and we will have 80% power to detect a correlation coefficient as small as -0.38. With an n of 17/group, we will have 95% power to measure a similar change in mitochondrial DAG and sphingolipids as we have observed in our pilot data after the weight loss or exercise interventions using pairwise comparisons in ANOVA models using the Tukey procedure. The type 1 error rate (alpha) will be set at 5% for all comparisons.

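### Aims 1 and 2 compare changes by an arm-only one-way ANOVA, which is valid; adding the baseline value and the randomisation strata would usually be more precise at small cost.

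*Combined protocol and SAP*

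**What the plan says.** The outcomes are changes. Section IV.A lists for Aim 1: "Change in insulin sensitivity, change in sarcolemmal Di-C18:0 DAG and C18:0 ceramide, change in PKCepsilon and PP2A activity". Aim 2 is defined in the same way.

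Section IV.F, Aim 1, says that the data on changes "will be analyzed using a one-way Analysis of Variance (ANOVA) to examine overall differences between the intervention groups", followed by Tukey's procedure for pairs of arms. Aim 2 repeats this: changes between groups "will be analyzed using a oneway ANOVA", again with Tukey. Both sentences are loosely worded. I read them as comparing change scores between the three arms, which is the only reading that fits a one-way ANOVA with Tukey contrasts. The only adjustments named are for multiplicity (Tukey and Benjamini-Hochberg). No section names a baseline or stratum covariate.

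Section IV.C describes "block randomization by sex and pre-diabetes strata equally across intervention groups" and the order of events: "After the baseline clamp, subjects will be randomized into one of three interventions for three months". The baseline values and the strata are therefore pre-treatment and already in hand for every participant.

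On size, Aim 1 states: "Pilot data showed sarcolemmal C18:0 ceramide decreased 0.041 ng/ug protein with a SD of .02 after the combined intervention", and "With an n of 17/group we will have 84.6% power to measure a similar change in sarcolemmal DAG and sphingolipids". Aim 2 states: "With an n of 17/group, we will have 95% power to measure a similar change in mitochondrial DAG and sphingolipids".

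**The concern.** A change score fixes the slope on baseline at 1, whereas a model with baseline as a covariate estimates it. When the true slope is not 1, the change score carries variance that the covariate would remove. The same applies to sex and glycaemic stratum if they predict the change; a stratum effect on level alone cancels in a change score. Leaving out prognostic strata that are balanced across arms also makes the arm-only test conservative.

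At stake is the width of the between-arm intervals with 17 completers per arm and many primary outcomes. The covariates are already collected, so any gain costs no participants.

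**Working it through.** **Inputs.** Three arms, 17 completers each, 51 in total (IV.C, IV.F); alpha 5%, taken as two-sided; Tukey. Pilot change 0.041 and SD .02 (IV.F, Aim 1), with the control change taken as zero. Assumed, because the documents give neither: rho = correlation of pre and post values; r = SD post / SD pre.

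**1. The plan's own figure.** Arm-only residual df = 51 − 3 = 48; Tukey critical value, on the t scale, 2.418. If 0.041 and .02 are the mean and SD of change, d = 0.041/0.02 = 2.05 and pairwise Tukey power is 99.97%, not the stated 84.6%. The planned half-width is 2.418 × 0.02 × √(2/17) = 0.0166 ng/µg protein. The stated 84.6% corresponds to d = 1.185, and the 95% in Aim 2 to d = 1.406. Because 84.6% does not follow from the pilot figures, I work with half-widths, which do not depend on it.

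**2. Effect of adding baseline.** Var(adjusted)/Var(change) = r²(1 − rho²)/(1 + r² − 2·rho·r). This never exceeds 1, and equals 1 when r = 1/rho. With r = 1 it reduces to (1 + rho)/2. Estimating the slope costs one df (48 to 47, critical value 2.420) and an expected imbalance factor of 1 + 1/46. Example, r = 1 and rho = 0.5: √(0.75 × 1.0217) × 2.420/2.418 = 0.88.

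**3. Adding uninformative two-level strata that are unbalanced among completers.** 45 df (critical value 2.424), imbalance factor 1 + 3/44.

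Half-width relative to plan, at rho 0.3 / 0.5 / 0.7 / 0.9:

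| SD ratio r | Baseline only | Baseline + two uninformative, unbalanced strata |
|---|---|---|
| 0.8 | 0.72 / 0.76 / 0.80 / 0.79 | 0.73 / 0.78 / 0.82 / 0.81 |
| 1.0 | 0.82 / 0.88 / 0.93 / 0.99 | 0.84 / 0.90 / 0.95 / 1.01 |
| 1.3 | 0.91 / 0.97 / 1.01 / 0.97 | 0.93 / 0.99 / 1.03 / 0.99 |
| 1.5 | 0.94 / 0.99 / 1.01 / 0.89 | 0.97 / 1.02 / 1.03 / 0.91 |

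**4. Worst case (r = 1/rho and strata uninformative).** Factor = (critical-value ratio) × √(imbalance factor):
- baseline only: (2.4201/2.4185) × √(1 + 1/46) = 1.011
- with two-level glycaemic stratum, balanced: (2.4236/2.4185) × √(1 + 1/46) = 1.013
- two-level, unbalanced: (2.4236/2.4185) × √(1 + 3/44) = 1.036
- three-level, unbalanced (44 df): (2.4255/2.4185) × √(1 + 4/43) = 1.049

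Break-even is 1 − 1/factor². Baseline alone pays for itself once it explains about 2.3% of the within-arm variance of change. The full two-level model needs about 2.5% (balanced) or 6.8% (unbalanced) jointly.

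As an illustration at d = 1.185, worst-case power falls from 84.6% to 83.7% with baseline only. With the full model it is 83.6% (balanced two-level), 81.7% (unbalanced two-level) or 80.7% (unbalanced three-level).

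**5. Validity.** In simulation, with two balanced binary strata each shifting the change by 0 / 0.3 / 0.5 / 0.8 SD, the arm-only family-wise error was 5.2 / 4.6 / 3.6 / 2.1%. Error is controlled, and the test becomes conservative as the strata become more prognostic.

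**6. Different SD ratios by arm.** Assume rho = 0.9 and r = 1 / 1 / 1.62 for control / exercise / diet (1.62 borrows the 62% rise in the diet pilot, IV.C). The slopes of change on baseline, r·rho − 1, are −0.10, −0.10 and 0.458, so the common slope is about 0.086. For exercise versus control, the variance per person goes from 2(1 − 0.9) = 0.20 to 1 + 1.086² − 2(0.9)(1.086) = 0.225, and √(0.225/0.20) = 1.06. Simulation, which also includes the noise in estimating the slope, gives a true standard error about 8% larger. The nominal pooled width does not change, so the model does not show this loss.

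**The case against.** The strongest reply is that nothing here is wrong. A prespecified change-score ANOVA with Tukey controls error, and a sometimes better alternative is a preference. That stands. A reader might infer that the arm-only analysis is biased or that omitting the stratification factors invalidates it. The documents do not support that: allocation is randomised, and the error rate is at or below nominal.

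A reader might also infer that the trial is underpowered without adjustment. On the plan's own 0.041 and .02, power is already 99.97%, so for that lipid only precision can improve. Powers that start from 84.6% or 95% are conditional illustrations; the inputs to the Aim 2 figure lie in figures that are not reproduced.

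Third, it is tempting to set up to 28% narrower against 1% wider. The 28% is the best cell (r = 0.8, rho = 0.3), and the 1% holds for baseline alone with one SD ratio in every arm. The model recommended here can cost 3.6% to 4.9% if the strata are unbalanced after the expected 25% dropout. Ratios above 1 are plausible on the raw scale, given the pilot's 62% rise in insulin sensitivity and the stated wish for a spread of changes (IV.E); there the gain is often small. The planned log transformation may bring the ratio nearer 1. Step 6 shows that a common slope can harm one contrast in an extreme case. All of this limits the gain without reversing the usual direction.

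Finally, the pooled Pearson correlations, which the plan lists first and powers separately, are untouched.

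**Conclusion.** The point holds as an optional efficiency improvement and not as an error. With baseline added and r = 1, intervals are 1% to 18% narrower over rho 0.9 to 0.3; at r = 1.3 to 1.5 they range from 11% narrower to 1% wider. If the covariates are uninformative, the full model costs about 1.3% in width with strata balanced among completers, and 3.6% (two-level) to 4.9% (three-level) otherwise. Baseline is the strongest part of the proposal; the case for the strata depends on how well they predict change.

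The results rest on assumed rho and r, 17 completers per arm, and a common r across arms. Covariates would not cure other threats, such as analysing completers or removing exercise participants who move more than 2 kg from starting weight (IV.E).

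**What to change.** In section IV.F, Aims 1 and 2, keep change as the outcome. Prespecify as covariates the baseline value of the same variable, sex, and the glycaemic stratum exactly as coded in the randomisation. Report Tukey-adjusted differences of adjusted means. Where the plan log-transforms, put change and baseline on the log scale. Modelling the post value with the same covariates gives the identical arm contrast, so the outcome definitions in IV.A need no change.

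One item must be settled first: section IV.B admits people with type 2 diabetes, but the strata in IV.C are named only as sex and pre-diabetes. The sponsor should state where those participants fall.

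The cost is SAP wording and three degrees of freedom with a two-level glycaemic stratum (48 to 45), or four with three levels (48 to 44). No new data or participants are needed. The covariates should be fixed before outcome data are seen, because choosing them later would weaken the plan's claim to an a priori analysis.

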to insulin resistance. The sum of all sarcolemmal disaturated 1,2-DAG species were significantly greater in T2D compared to lean volunteers (Figure 2A), and was inversely related to insulin sensitivity (Figure 2B). Notably, 1,3-disaturated DAG content was not different between groups revealing isomer specificity. We previously showed that membrane di-saturated DAG content predicted PKC activation and insulin resistance (26). These data agree and suggest that sarcolemmal DAG containing saturated acyl side chains represent membrane accumulation of DAG that is particularly negative for insulin sensitivity.

PKC ϵ activity is increased in obesity and T2D. We

measured the membrane/cytosol ratio of PKC ϵ , which is commonly used as a surrogate for PKC activity. We found significantly greater PKC ϵ activation in obese and T2D subjects compared to lean controls (Figure 3), with no significant differences found for PKC β II, δ , and θ isoforms. These data are consistent with greater PKC activation from sarcolemmal DAG accumulation.

Sarcolemmal C18:0 ceramide accumulates in insulin resistance. Of the 9 sarcolemmal ceramide species measured, only C18:0 ceramide was significantly greater in T2D compared to lean (Figure 4A), and was inversely related to the rate of glucose disappearance during an insulin clamp (Figure 4B). In a pilot study sarcolemmal C18:0 ceramide decreased by 21% after a combined weight loss

and exercise training intervention. These data parallel a recent publication by our lab showing C18:0 muscle ceramides significantly related to insulin resistance in a different cohort (27). C18:0 ceramide antagonizes an inhibitor of PP2A, resulting in increased PP2A activity (28). Combined, these data suggest that sarcolemmal C18:0 ceramide may promote insulin resistance, and due to the location may explain the canonical pathways of ceramide induced insulin resistance, including activation of PP2A activity, and inhibition of AKT phosphorylation in response to insulin.

Mitochondrial/ER ceramide accumulates in insulin

resistance. Mitochondrial ceramide content was greater in T2D compared to lean individuals, which is largely explained by C22:0 and C24:0 species (Figure 7A). Total ceramide content was inversely related to

insulin sensitivity (Figure 7B). These data are consistent with the hypothesis that mitochondrial ceramides promote insulin resistance.

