Mitochondrial/ER ceramides decrease after insulin sensitizing lifestyle intervention - Pilot data for a combined weight loss/exercise training intervention show decreased whole cell ceramide content, as shown before (11; 15) (Figure 8). However, the decrease in whole cell ceramide content comes only from a decrease in mitochondrial/ER ceramide. These data point to an important role of mitochondrial/ER ceramides on insulin sensitivity in vivo.

Mitochondrial/ER DAG accumulates in lean insulin sensitive individuals. Preliminary data show mitochondrial/ER 1,2- and 1,3-DAG were

Figure 2. Sarcolemmal di-saturated DAG content by group (A), and by insulin sensitivity (B) in lean, obese, and type 2 diabetics. Values are means +/- SEMC # significantly different than lean, p<0.05.

Figure 3. PKCE activation in lean, obese, and type 2 diabetics. Values are means +/- SEM. #= significantly different than lean, p<0.05.

Figure 4. Sarcolemmal C18:0 ceramide content by group (A), and by insulin sensitivity (B) in lean, obese, and type 2 diabetics. Values are means +/- SEM. #= significantly

different than lean, p < 0.05.

higher in lean individuals compared to obese or type 2 diabetic volunteers (Figure 9), with the greater DAG content distributed over most species. These data are counterintuitive, but may reflect the greater content of mitochondria in lean individuals compared to obese volunteers with and without diabetes, and/or increased mitochondrial fission/fusion (29; 30).

Mitochondrial/ER DAG increase after weight loss and exercise training.

Preliminary data from a weight loss and exercise training intervention show an increase in mitochondrial/ER 1,2-DAG after the intervention (Figure 10). These data are consistent with some reports in the literature where DAG concentration was increased in endurance trained athletes (13). These data agree with Figure 9 and suggest mitochondrial/ER DAG accumulation may be a previously unrecognized adaptation to exercise training and/or weight loss.

Insulin resistant muscle accumulates long chain acyl-carnitines and shows oxidative

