Exercise training and weight loss will differentially change DAG and sphingolipid content (11), revealing distinct changes in lipid localization, cellular signaling, metabolic function, and improvements in insulin sensitivity. We are expecting a 25% dropout rate, and are powered to complete testing on 17 individuals per group (51 total individuals). Subjects will be tested 48 hours after the last exercise bout to minimize acute exercise effects on insulin sensitivity. Women will be pre-menopausal and tested during the follicular phase (days 1-10) of the menstrual cycle to control for effects on insulin sensitivity.

Preliminary screening- Subjects will arrive after an overnight fast to the outpatient Clinical Translational Research Center (CTRC), and a fasting blood sample will be taken for a standard lipid panel, fasting glucose, TSH, and HbA1c. Women will take a pregnancy test. A physician will perform a history and physical, and subjects will fill out a dietary questionnaire, the NIH Dietary History Questionnaire II (DHQII), and the IPAQ physical activity questionnaire (33).

Strength and Exercise testing, body composition, maximal mitochondrial respiration, and MRI – Eligible subjects will undergo a Kin-Kom isokinetic dynamometer quadriceps strength test, Balke treadmill test to measure maximal work capacity (VO₂max) (34), a DEXA scan to determine body composition, a non-invasive test of maximal mitochondrial respiration, and MRI scan to measure leg muscle and fat mass, and liver fat content. During the maximal mitochondrial respiration test, volunteers will lie down on a table, and we will have a near infrared spectrometer measurement unit strapped to their leg. This unit uses a laser to measure the oxygen levels in the muscle. A blood pressure cuff will be wrapped around their upper thigh. To start the test, we will ask volunteers to make a muscle contraction for 20 seconds, after which we will intermittently inflate and deflate the blood pressure cuff every 5-10 seconds over a 5 minute period. This test will then be repeated. The total time for this test is 30 minutes.

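### The correlation power in Aims 1 and 2 borrows r from cross-sectional lipid levels although the planned analysis correlates changes, and Aim 2's 99% is an arithmetic error (about 90%)

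*Combined protocol and SAP*

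**What the plan says.** Section IV.F, Aim 1, plans Pearson coefficients in the whole study group: "Correlations between the change in sarcolemmal DAG and sphingolipid species and the change in insulin sensitivity". It describes its power analysis as based on changes in sarcolemmal lipids, then claims "92% power to detect a Pearson correlation coefficient similar to our preliminary data (Figure 2B, r= -0.45"), and 80% power for a coefficient as small as -0.38. Alpha is 5%; sidedness is not stated.

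Aim 2 repeats the scheme for mitochondrial/ER lipids. It says that power rests on pilot changes (Figures 8 and 10), then claims 99% power for a coefficient "as large as that observed in our preliminary data (Figure 7B, r= -0.44"), and again 80% at -0.38.

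The Figure 2 caption in section III reads "Sarcolemmal di-saturated DAG content by group (A), and by insulin sensitivity (B) in lean, obese, and type 2 diabetics". The accompanying text says "The sum of all sarcolemmal disaturated 1,2-DAG species were significantly greater in T2D compared to lean volunteers (Figure 2A"). For Figure 7B the section III text says that total mitochondrial ceramide content was inversely related to insulin sensitivity, directly after a comparison of type 2 diabetic with lean people.

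On the population, section IV.B says that obese men and women with BMI 30-40 "will be recruited for this study who are between 30-50 years of age and sedentary", and that "Individuals with normal glucose tolerance (NGT), pre-diabetes, and newly diagnosed type 2 diabetes will be enrolled". Section IV.C says that the study is "powered to complete testing on 17 individuals per group (51 total individuals").

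**The concern.** A power statement needs the effect size of the quantity that will be tested. Here the tested quantity is a correlation of two changes within an obese sample. The quoted r values are correlations of two levels, and for Figure 2B the sample also includes lean people. A level correlation can arise largely from stable differences between people and need not reappear when each person is compared with himself or herself. Section II makes a similar point: it calls the response of these lipids to insulin-sensitising interventions variable and cites studies in which lipid content and insulin sensitivity did not go together.

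The correlation is the first analysis listed in both aims. A non-significant result would be read against claimed power of 92% or 99%, as though a relationship of the preliminary size had been all but excluded. Neither figure supports that reading.

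**Working it through.** **Inputs.** n = 51 completers (17 per group × 3); alpha 5%, taken as two-sided because that reproduces the Aim 1 figure; r = -0.45 (Aim 1) and -0.44 (Aim 2).

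**Formula.** Fisher z: power = Φ(atanh|r| × √(n − 3) − 1.96), with √48 = 6.928.

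**The plan's own figures.**
- Aim 1, |r| = 0.45: 0.4847 × 6.928 − 1.96 = 1.398, so power is 91.9% (simulation of the t-test of r: 92.4%). The stated 92% reproduces.
- Both aims, |r| = 0.38: 0.4001 × 6.928 − 1.96 = 0.812, so power is 79.2% (simulation 80.0%). The stated 80% reproduces.
- Aim 2, |r| = 0.44: 0.4722 × 6.928 − 1.96 = 1.312, so power is 90.5% (simulation 91.0%). The stated 99% does not reproduce. A one-sided test gives 94.8%. All 69 enrolled people, two-sided, give 97.0%. Reaching 99% needs n of about 86, or |r| of about 0.55 at n = 51.

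The two aims also conflict without any calculation: at the same n and alpha, the smaller |r| of 0.44 cannot have more power than 0.45.

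**Do the r values estimate the planned quantity?**

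| | Preliminary r | Planned analysis |
|---|---|---|
| Variables | lipid content and insulin sensitivity, as levels | change in each |
| People | Figure 2B: lean, obese, type 2 diabetic | BMI 30-40; normal tolerance, pre-diabetes, new type 2 diabetes |
| Structure | cross-section | three randomised arms, pooled |

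They differ on every row. The pilot intervention data are used in IV.F only for the group comparisons. No correlation of changes is reported anywhere.

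**What the design supports at n = 51, whatever the source of r.**

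| True \|r\| between changes | 0.45 | 0.40 | 0.38 | 0.35 | 0.30 | 0.25 | 0.20 |
|---|---|---|---|---|---|---|---|
| Power | 91.9% | 83.5% | 79.2% | 71.6% | 57.3% | 42.4% | 28.9% |

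**Which way could r move?** The documents do not give these quantities, so each line is an assumption.
- Loss of the lean group: if the predictor's SD falls to a fraction u of its preliminary value, r′ = ru/√(1 − r² + r²u²). From 0.45, u = 0.8 gives 0.374 and 78% power; u = 0.6 gives 0.289 and 54%.
- Error in change scores: if it multiplies r by 0.8, r is 0.36 and power 74%; by 0.6, 0.27 and 48%.
- Between-group contrast in the preliminary data: if groups explain a share f of the variance of both variables, perfectly inversely, the within-group |r| is (0.45 − f)/(1 − f). For f = 0.1, 0.2, 0.3 this is 0.39, 0.31, 0.21, with power 81%, 61%, 33%.
- Between-arm contrast in the trial acts the other way. If arms explain a share g of both changes, perfectly inversely, the pooled |r| is g + (1 − g) × within-group |r|. With f = 0.2 and g = 0.2: 0.2 + 0.8 × 0.3125 = 0.45, and power is back at 92%.

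**The case against.** The strongest reply is that pooling the arms builds in contrast that the downward scenarios leave out. IV.F assumes no change in the control arm, and IV.E counts on differing success of the interventions to spread the changes. As shown above, an equal 20% share restores r = 0.45. This stands. A reader might infer that the trial's power is below 92%, or that 51 completers are too few. The documents do not support either inference, because the size and direction of the shift cannot be determined from them.

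Second, the difference in population is narrower than it may look. People with newly diagnosed type 2 diabetes are enrolled under IV.B, so what is lost is the lean group, and the within-group formula removes more contrast than the trial does. The available text also has no caption for Figure 7B. That it shows levels is clear from section III, but its exact sample is not.

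Third, the plan already states 80% power at -0.38, which does not depend on preliminary data, and the primary outcomes in IV.A are changes, not correlations. Both are true and limit the importance of the point. Nor would a null result be uninformative if reported with an interval: the half-width on the z scale is 1.96/6.928 = 0.283, so an observed -0.20 (z = -0.203) has limits of -0.486 and 0.080 in z, or about -0.45 to 0.08 in r.

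It could also be said that the reference to changes in IV.F was meant for the group comparisons alone. That would explain the wording, but the correlation claims would still have no basis in changes. None of these replies rescues the 99%.

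**Conclusion.** The point holds in two parts. First, the power tied to preliminary data in both aims is unsupported: the cited correlations concern levels, the tests concern changes, and nothing in the documents links the two. Aim 1's 92% is correct arithmetic conditional on a change correlation of -0.45. The 81%, 61% and 33% figures above are one side of an undetermined range and should not be quoted as the trial's power. Second, Aim 2's 99% is wrong on its own inputs; it should be about 90.5% (Fisher z, n = 51, two-sided 5%), an overstatement of about 8.5 percentage points. The second part rests only on the stated n, r and alpha; a one-sided test would not rescue it. Sample size, outcomes and tests are unaffected, so this is a correction to stated figures and to how a null correlation will be interpreted.

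**What to change.** In IV.F, Aims 1 and 2:
- Delete the power statements tied to Figures 2B and 7B. Alternatively, keep them with the r values labelled as assumptions taken from cross-sectional levels, and correct Aim 2's 99% to about 90%.
- Make the detectable correlation the main statement, for example: *with 51 completers and a two-sided 5% test, power is about 80% for |r| = 0.38 between changes, 57% for 0.30 and 29% for 0.20.*
- Report each change correlation with its 95% confidence interval.
- Use a pilot correlation of changes only if fractionated lipids and insulin sensitivity were measured before and after in the same pilot participants, which the documents do not show. State its n, and note that the pilot lipid changes came from a combined weight-loss and exercise intervention, which is not an arm of this trial.

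The cost is a few sentences of the plan and, if paired pilot data exist, one calculation. Recruitment and procedures do not change. The drawback is that the stated power, Aim 2's in particular, looks less favourable.
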